Thus, it is crucial to identify strategies to enhance motor learning in people with PD. Recent studies have accumulated evidence to show that acute (single bouts of) cardiovascular exercise can facilitate motor skill learning. However, this evidence is mainly derived from studying healthy individuals. In a first study including PD patients, we recently found improved motor memory consolidation, but not skill acquisition, when practice was preceded by a single bout of cardiovascular exercise.

These results suggest that acute exercise may enhance motor memory formation processes, but could potentially interfere with motor skill acquisition when performed prior to practice. Consequently, the present study investigates whether performing a single bout of cardiovascular exercise immediately following skill practice will enhance motor memory consolidation without affecting skill acquisition in PD.

Aims/Hypothesis

The main question of the study is whether a single bout of moderate-intense aerobic exercise, performed immediately following motor skill practice, facilitates motor memory consolidation in Parkinson Disease.

Hypothesis:

1. An acute cardiovascular exercise bout performed immediately following skill practice leads to increased motor skill consolidation (larger offline gains) after 24 h and 7 days.

Outcome measures

Motor skill learning

A dynamic balance task will be used to assess participants' motor learning performance. The device consists of a 107 x 65 cm wooden platform (stability platform; Lafayette Instrument Europe; Loughborough, United Kingdom), which is mounted on a fulcrum and has a maximum deviation of 15° to either side. Participants are required to stand with both feet on the platform and try to keep the platform as close to the horizontal as possible during a 30 seconds trial. A millisecond timer measures angular displacement from horizontal during each 30 seconds trial. Participants will be secured with a safety harness and instructed to stand in a comfortable position.

Primary outcome measure – Precision

Description: Time in balance (angular displacement $\pm 5^\circ$ from horizontal) during each 30 seconds trial.

Secondary outcome measure – Variability:

Description: Root mean square error (average angular deviation from horizontal) during each 30 seconds trial.

Memory consolidation (offline learning):

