To assess motor skill consolidation (offline learning) primary and secondary outcomes will be calculated as change scores from the final performance (last practice block) during skill practice to skill performance in a 24-hour and 7-day retention test, respectively (Figure 1).

Study design

In an experimental trial, participants will be randomly allocated to one of two groups (Figure 1). Each experimental arm includes i) a pre-examination 2 - 14 days before ii) an acquisition session where the motor skill will be practiced, followed by a retention test iii) 24 \pm 2 hours and iv) 7 days later (Figure 1). On acquisition day, the experimental group will perform a single bout of aerobic exercise (cycle ergometer) immediately following motor practice, whereas the control group will rest.

Conditions:

- 1. Experimental condition:** Participants in the experimental group will practice the ***motor learning task*** followed by a single bout of moderate-intensity ***aerobic exercise*** on a cycle ergometer during acquisition day.
- 2. Control condition:** Participants in the control group will practice the ***motor learning task*** followed by a ***seated rest*** period during acquisition day.

[figure not shown]

Fig. 1 Study design.

Aerobic exercise bout:

The acute cardiovascular exercise bout comprises a 5-minutes warm-up (intensity will be progressively increased until target intensity), followed by 25 minutes of pedaling at 60–80 rpm and 60% of maximal power output reached in a graded exercise test during pre-examination.

Rest:

The resting phase includes seated rest on a chair for 30 minutes. Participants will be permitted to read during the 30 minutes.

Motor skill practice:

Irrespective of group allocation, participants will follow the identical skill practice routine. On acquisition day, participants will perform a familiarization trial followed by 15 practice trials (30 seconds), clustered into 5 blocks of 3 trials, with 60 seconds rest between trials and 120 sec rest between blocks. 24 hours as well as 7 days later, participants will perform a retention test consisting of one familiarization trial (to account for potential warm-up effects) and one practice block (3 trials) on the stability platform, respectively.

Study population

Inclusion criteria:

Patients are eligible if they have

- a Hoehn and Yahr score of ≤ 3 ;
- a score of ≤ 1 in the UPDRS item 'postural instability';
- are able to stand and walk independently; and

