- are not familiar with the motor task.

Exclusion criteria:

Criteria for exclusion are

- higher level of cognitive impairment indicated by a score of <21 in the Montreal Cognitive Assessment (MoCA);
- other clinically relevant neurological, internal or orthopedic conditions besides Parkinsonism that would interfere with the exercise paradigm or motor learning task;
- (musculoskeletal conditions or surgery 1 year before the study enrolment;
- smoking>10 cigarettes/day or drinking>6 cups of coffee/day or >50 g of alcohol (equivalent of two glasses of wine) consumption/day (Winter et al., 2007).

Statistical analysis plan

Power calculation:

Considering data from similar previous experiments, an a priori estimation of the required sample size for the primary analysis was performed using the statistics program G*Power (version 3.1.9.2). Accordingly, to identify a significant interaction effect for offline learning (change from end of skill acquisition to 24h/7-day retention test) with large effect sizes ($f=0.58$; according to previous studies) with a statistical power of 80% and a significance level of $p\leq.05$, 26 subjects ($n=13$ per group) need to be included.

Statistical analysis:

The effect of aerobic exercise on motor skill learning will be examined by separate mixed ANOVAs testing for the between-subject factor Condition (aerobic exercise, rest) and the within-subject factor Blocks. Two separate ANOVAs will be performed for 24-hour and 7-day retention, respectively. Specifically, effects of aerobic exercise on offline learning will be analyzed in a 2 (aerobic exercise, rest) x 2 (last practice block during acquisition, first block during 24-hour/ 7-day retention test) model.

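### Optional: test the exercise effect adjusted for the last practice block rather than by the Condition x Block interaction; the planned test is valid, but adjustment may add power at little risk

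*Combined protocol and SAP*

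**What the plan says.** The Memory consolidation paragraph under Outcome measures defines the outcomes as "change scores from the final performance (last practice block) during skill practice to skill performance in a 24-hour and 7-day retention test". The hypothesis is that exercise "leads to increased motor skill consolidation (larger offline gains) after 24 h and 7 days".

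The Statistical analysis section plans "separate mixed ANOVAs testing for the between-subject factor Condition (aerobic exercise, rest) and the within-subject factor Blocks", one for each retention time, and specifies for offline learning a "2 (aerobic exercise, rest) x 2 (last practice block during acquisition, first block during 24-hour/ 7-day retention test) model". It names no covariate. The Power calculation section sizes the trial "to identify a significant interaction effect for offline learning (change from end of skill acquisition to 24h/7-day retention test"), with f = 0.58, 80% power and a 5% level, giving 26 participants, 13 per group.

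Two statements in the Study design section fix the timing. On practice: "Irrespective of group allocation, participants will follow the identical skill practice routine". On treatment: the experimental group "will perform a single bout of aerobic exercise (cycle ergometer) immediately following motor practice, whereas the control group will rest".

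**The concern.** With two blocks, the Condition x Block interaction is a two-sample t-test on retention minus last block. Subtracting the full last-block value assumes that a participant who ends practice one unit higher will also be one unit higher at retention. If the true slope is below 1, as it is whenever the SDs are equal and the correlation is imperfect, the subtraction over-corrects. The estimate then carries noise that a fitted slope would remove.

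The last block comes before the arms differ in treatment and follows identical practice, so it qualifies as a baseline covariate. Two things are at stake. One is power, in a trial sized only just above its 80% target. The other is how far the result of a trial with 13 per arm depends on which arm happened to end practice lower.

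**Working it through.** **Inputs from the documents.** f = 0.58, two-sided 5% level (an F test with two groups), 13 per arm, total N = 26. For two equal groups d = 2f = 1.16, in SDs of the change score.

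**Inputs not in the documents (assumed, with ranges).** rho is the correlation of the last block with the retention block. k is the retention SD divided by the last-block SD, with the last-block SD set to 1.

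**1. The plan's own figure.** Noncentrality = f² x N = 0.3364 x 26 = 8.75 on 1 and 24 df, which gives power 0.810. N = 24 gives 0.775. So 26 is the smallest even total that reaches 80%, and the stated figure reproduces.

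**2. Same target.** If (retention − last) = group + b x last, then retention = group + (b + 1) x last. Adjusting the change score and adjusting the retention value give the same group coefficient. Under randomisation it estimates the same mean difference in offline gain as the interaction.

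**3. Variance.**
- Change score: 1 + k² − 2 rho k.
- Adjusted: k²(1 − rho²) x (1 + 1/22); the last factor is the average cost of estimating the slope.
- Since k²(1 − rho²) = (1 + k² − 2 rho k) − (1 − rho k)², the ratio is (23/22) x [1 − (1 − rho k)²/(1 + k² − 2 rho k)].
- The ratio cannot exceed 23/22 = 1.045, reached when rho k = 1. With k = 1 it is (23/22)(1 + rho)/2, for example 1.045 x 0.75 = 0.784 at rho 0.5. It equals 1 at rho = 44/23 − 1 = 0.91.

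**4. Power at N = 26.** The planned test has 0.81 throughout. Adjusted power uses a noncentral t on 23 df, averaged over chance imbalance:

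| Retention SD relative to last block | rho 0.5 | 0.7 | 0.8 | 0.9 |
|---|---|---|---|---|
| 20% smaller | 0.96 | 0.94 | 0.93 | 0.94 |
| equal | 0.89 | 0.85 | 0.83 | 0.81 |
| 20% larger | 0.84 | 0.80 | 0.79 | 0.80 |
| 40% larger | 0.81 | 0.79 | 0.80 | 0.85 |

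With equal SDs, power is 0.80 at rho 0.95. The floor over every rho and k is 0.791, a loss of 0.810 − 0.791 = 0.019. For scale, the planned test would need N = 32 to reach 0.89, so the gain at rho 0.5 with equal SDs is worth about 6 participants. In simulation both tests held the 5% level.

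**5. Chance imbalance.** Let u be the last-block difference, exercise minus rest, in SDs. Its standard error is sqrt(2/13) = 0.392, so P(|u| > 0.5) = 2 x [1 − Φ(0.5/0.392)] = 0.202, or about 10% in each direction. With k = 1 and true effect delta, the change-score estimate is centred on delta − (1 − rho)u. The adjusted estimate is centred on delta. For time in balance, where higher is better:

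| Setting | rho 0.5 | 0.7 | 0.8 |
|---|---|---|---|
| Planned power, exercise arm 0.5 SD higher | 0.62 | 0.67 | 0.70 |
| Planned power, exercise arm 0.5 SD lower | 0.95 | 0.93 | 0.91 |
| Adjusted power, either way | 0.88 | 0.84 | 0.82 |
| Planned two-sided error, imbalance exactly 0.5 SD | 6.4% | 5.9% | 5.6% |
| Planned two-sided error, averaged over imbalance above 0.5 SD | 10.8% | 8.5% | 7.3% |
| Planned two-sided error, averaged over imbalance below 0.5 SD | 3.5% | 4.1% | 4.4% |

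The two averages combine to the nominal level; at rho 0.5, 0.202 x 10.8% + 0.798 x 3.5% = 5.0%. The adjusted test stays at 5% whatever the imbalance.

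**The case against.** The plan is consistent with itself: hypothesis, outcome, test and sample size all refer to the change score, and the test holds its level over randomisation. Choosing ANCOVA is a choice between two valid analyses. The benefit also rests on quantities that the documents do not give. With equal SDs nothing is gained above rho of about 0.91, and the loss there grows from 0.9 points at rho 0.95 to 1.8 as rho approaches 1. With a retention SD 20% larger, power is lost for rho between 0.68 and 0.92; with one 40% larger, between 0.53 and 0.83. Adjusted power can then fall just under the 80% target, which the planned test meets. All of this stands, and it is why the point is optional.

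Three narrower points also stand. The 2-point bound is for 26 analysed. The worst-case loss at the design effect is 2.1 points with 24, 2.4 with 22 and 2.8 with 20, and the sample size section states no dropout allowance. The linearity and common-slope checks are weak at this size: a slope difference of 0.3 between arms is detected with power of only 0.12 to 0.21 for rho 0.5 to 0.8. Switching models on the strength of such a check would be worse than either analysis. Finally, the present power statement is for the interaction and would have to be rewritten.

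The error inflation under imbalance is conditional: the roughly 80% of randomisations with smaller imbalance have error below 5%. It shows sensitivity to chance and not a failure of the planned test.

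**Conclusion.** The point holds as an optional improvement. The planned interaction test is valid. Adjusting for the last block answers the same question. With equal SDs it gains about 8, 4 and 2 points of power at rho 0.5, 0.7 and 0.8, and nothing above about 0.91. With 26 analysed it costs at most about 2 points for any rho and SD ratio. Separately from average power, it stops the result from depending on which arm ended practice lower.

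This rests on reading f = 0.58 as d = 1.16 change-score SDs, on normal errors with a common linear slope, and on the last block being unaffected by allocation. The last is supported by the identical practice routine, although the documents do not say when participants learn their arm. Confidence in the size of the gain is moderate, because rho and the SD ratio are unknown.

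**What to change.** Before any data by group are seen, prespecify for each retention test (24 hours and 7 days) the linear model: retention-block value = group + last-practice-block value. The group coefficient replaces the Condition x Block interaction as the test of the exercise effect. Time in balance stays primary. The secondary outcome ("Root mean square error (average angular deviation from horizontal) during each 30 seconds trial") gets the same model after it. Keep reporting the change scores and the Block effect from the 2x2 ANOVA as supporting results.

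State that the adjusted model decides whatever the linearity and slope checks show, and report those checks as sensitivity analyses. They matter because time in balance is bounded between 0 and 30 s. Restate the power calculation over an assumed range of rho and SD ratio.

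The cost is a few lines of SAP text, the power restatement, one line of code and one error degree of freedom (23 instead of 24). Estimating the slope adds about 4.5% to the variance (1/22), which is already included in the power figures. No new data or visits are needed.

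### The retention analysis is an unadjusted change-score test; ANCOVA on the last practice block would usually be more precise, with an uncertain further gain from practice blocks 1–4

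*Combined protocol and SAP*

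**What the plan says.** Under Motor skill practice, on acquisition day "participants will perform a familiarization trial followed by 15 practice trials (30 seconds), clustered into 5 blocks of 3 trials". Both groups do the same: "Irrespective of group allocation, participants will follow the identical skill practice routine". The cycling bout or the seated rest comes only after this practice. Each retention test has one familiarization trial and then "one practice block (3 trials) on the stability platform".

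Under Memory consolidation, offline learning is defined as the change from the last practice block to the retention test. The Statistical analysis section follows that definition with a "2 (aerobic exercise, rest) x 2 (last practice block during acquisition, first block during 24-hour/ 7-day retention test) model", fitted once for 24 hours and once for 7 days. No covariate is mentioned.

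The Power calculation assumes "large effect sizes ($f=0.58$; according to previous studies", "with a statistical power of 80% and a significance level of" .05, and concludes that "26 subjects ($n=13$ per group) need to be included".

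**The concern.** With two groups and two blocks, the Condition-by-Block interaction is a comparison of mean change scores. A change score is a baseline adjustment with the slope fixed at 1. If the last practice block and the retention block are less than perfectly correlated, as two 3-trial scores will be, all the noise in the practice block passes into the outcome. Estimating the slope by ANCOVA removes some of that noise.

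There is also further pre-intervention information. Blocks 1–4 hold 12 of the 15 scored practice trials (80%) on the same task, and they do not enter the retention comparison. To the extent that they reflect a participant's lasting skill, they help separate skill from chance variation in trials 13–15.

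At stake is the width of the interval for the exercise effect at both retention tests, in a trial with 13 per arm and no stated dropout allowance.

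**Working it through.** **Inputs.** From Power calculation: f=0.58, alpha 0.05, N=26 (13 per arm). From Motor skill practice: five practice blocks and one retention block per test, three trials each. Assumed, because the documents give none: the correlations between blocks. A block score is taken as the mean of its three trials, since the plan does not say how trials are combined.

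**The plan's own figure.** For the interaction read as a two-group test on change, d = 2f = 1.16, lambda = f² × N, and df = 1, N−2.
- N=24: lambda = 0.3364 × 24 = 8.07, power 77.5%.
- N=26: lambda = 0.3364 × 26 = 8.75, power 81.0%.

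So 26 is the smallest even N that reaches 80%, and the stated sample size reproduces on this reading.

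**Residual variances.** R is the retention block, B5 the last practice block, and M the mean of blocks 1–4.
- Planned change score: v0 = var(R) + var(B5) − 2cov(R,B5)
- ANCOVA on B5: v1 = var(R) − cov(R,B5)²/var(B5)
- ANCOVA on B5 and M: v2 = var(R) − c′V⁻¹c, where c holds the covariances of R with (B5, M) and V is their covariance matrix

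For q covariates, power uses lambda = f²N ÷ (v/v0) × (N−3−q)/(N−3), with df = 1, N−2−q. The last factor allows for chance covariate imbalance. The effect stays at 0.58 on the change-score scale throughout.

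**Worked case, constant block correlation r=0.7, unit variances.**
- v0 = 2(1−0.7) = 0.60
- v1 = 1−0.49 = 0.51, ratio 0.850; lambda = 8.746/0.850 × 22/23 = 9.84, df 23, power 85.2%
- v2 = 1 − 5r²/(1+4r) = 1 − 2.45/3.8 = 0.355, ratio 0.592; lambda = 8.746/0.592 × 21/23 = 13.5, df 22, power 93.9%

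Simulation of the same case (8000 runs) gave 81.0, 85.4 and 93.7%. Type I error was 4.6 to 5.3% across the simulated scenarios.

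**Range of structures** (planned test 81.0% in every row):

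| Assumed structure | v1/v0 | v2/v0 | Power, B5 only | Power, B5 + M | Added by blocks 1–4 (points) |
|---|---|---|---|---|---|
| Constant r=0.3 | 0.650 | 0.568 | 93.0% | 94.7% | about +2 |
| Constant r=0.5 | 0.750 | 0.583 | 89.2% | 94.2% | about +5 |
| Constant r=0.7 | 0.850 | 0.592 | 85.2% | 93.9% | about +9 |
| Constant r=0.9 | 0.950 | 0.598 | 81.1% | 93.7% | about +13 |
| Day-level variation, 0.5/0.1 | 0.841 | 0.717 | 85.5% | 89.1% | about +4 |
| Day-level variation, 0.6/0.2 | 0.846 | 0.795 | 85.3% | 85.7% | about 0 |
| Day-level variation, 0.7/0.2 | 0.875 | 0.842 | 84.2% | 83.7% | about 0 |
| Decay 0.8 per block, noise 0.2 | 0.833 | 0.819 | 85.9% | 84.7% | about −1 |
| Decay 0.9 per block, noise 0.2 | 0.875 | 0.823 | 84.2% | 84.5% | about 0 |
| Decay 0.95 per block, noise 0.4 | 0.839 | 0.708 | 85.6% | 89.4% | about +4 |
| Decay 0.9, no noise | 0.950 | 0.950 | 81.1% | 79.1% | about −2 |
| Decay 0.95, no noise | 0.975 | 0.975 | 80.1% | 78.1% | about −2 |

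Day-level rows give the persistent and within-day shares of single-trial variance; the rest is trial noise, divided by 3 in a block mean. Decay rows count retention as one step after block 5, with block-level noise as a fraction of true-score variance.

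**Separating the two gains.** At r=0.5, power goes from 81.0 to 89.2 to 94.2%: 8.2 points come from replacing the change score and 5.0 from blocks 1–4. At r=0.9 nearly all the gain comes from blocks 1–4. With decay 0.8 and noise 0.2, all of it comes from ANCOVA on the last block, and adding blocks 1–4 gives a little back.

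**The case against.** The plan is coherent. Its definition of offline learning, its power calculation and its test all refer to the same change from the last practice block, and the test is unbiased under randomisation. Thin margin above 80% is what any smallest-N calculation produces. All of this stands, so the point concerns efficiency only.

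A reader might infer that blocks 1–4 explain the whole loss of precision. The figures do not support that: part of the gain, and in some structures all of it, needs only the last block as a covariate.

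A reader might also infer that blocks 1–4 can hurt only if they carry no information. That is too narrow. With decay 0.8 per block and noise of 0.1 to 0.4, they lower residual variance by 1 to 3%, yet power falls by 0.6 to 1.6 points because the extra covariate costs more than it returns. Participants must be new to the task, so the early blocks lie on the learning curve and decaying correlation is credible.

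Finally, a reader might infer that blocks 1–4 go unused in the trial. The documents establish only that they are absent from the retention comparison. The general sentence on mixed ANOVAs names a factor Blocks, and the Background raises skill acquisition, so an acquisition analysis may use them, although none is spelled out.

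The objection that an adjusted model changes the question does not stand. Every covariate precedes exercise or rest, so the expected between-arm difference is the same quantity. This assumes that practice is not influenced by knowledge of the allocation; the documents do not say when allocation is disclosed.

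**Conclusion.** The point holds as a minor, low-cost improvement. The planned test is valid but usually less precise than an adjusted analysis of data already recorded. At N=26 and f=0.58, against 81% planned, last-block ANCOVA gives about 80 to 93% and the two-covariate model about 78 to 95%.

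The increment from blocks 1–4 should be stated separately. It is about +5 to +13 points if correlation between blocks is roughly constant at 0.5 or more, less at lower constant correlation (where last-block ANCOVA already captures most of the gain), about 0 to +4 with shared day-level variation, and about −2 to +4 if correlation decays across blocks. It is therefore uncertain and can be slightly negative.

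All these figures rest on assumed correlations and on block means of three trials. Nothing here shows bias, an invalid test or an insufficient sample size.

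**What to change.** In the Statistical analysis section, pre-specify for each retention test (24 hours, 7 days) an ANCOVA of the retention-block score on Condition, with the last practice block as covariate and the mean of practice blocks 1–4 as a second covariate. Report the adjusted between-arm difference with its 95% CI. Keep the 2 x 2 interaction as a supporting analysis. State how the three trials in a block are combined.

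Keep the last block as its own covariate. Replacing it with a single 15-trial mean departs from the definition of offline learning and can lose precision: under pure decay of 0.9 per block, power with that mean as the only covariate falls to 54%.

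The cost is a sentence or two of text and two degrees of freedom (one if only the last block is used). At worst that is about 2 to 3 power points against the planned test (81.0 to 78.1% with decay 0.95 and no noise). No patients, visits or trials are added. The choice must be fixed before results are seen.
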